5.6 Management Algorithms for Immuno-Oncology Agents

Immuno-oncology (I-O) agents are associated with adverse events that can differ in severity and duration than adverse events caused by other therapeutic classes. Nivolumab and ipilimumab are considered immuno-oncology agents in this protocol. Management algorithms have been developed to assist investigators in assessing and managing the following groups of adverse events: Gastrointestinal, Renal, Pulmonary, Hepatic, Endocrinopathies, Skin, and Neurological.

Early recognition and intervention are recommended according to the management algorithms; and in addition include ophthalmologic evaluations for any visual symptoms in order to evaluate for nivolumab or ipilimumab related uveitis.

The recommendations are to follow the algorithms in the nivolumab investigator brochure for immune related events; while the ipilimumab investigator brochure contains similar algorithms, the algorithms in the nivolumab brochure have been aligned to accommodate combinations as well as nivolumab monotherapy. Therefore, the algorithms recommended for utilization are in Appendix G for reference.

For subjects expected who require more than 4 weeks of corticosteroids or other immunosuppressants to manage an adverse event, consider the following recommendations

- Antimicrobial/antifungal prophylaxis per institutional guidelines to prevent opportunistic infections such as Pneumocystis jiroveci and fungal infections.
- Early consultation with an infectious disease specialist should be considered. Depending on the presentation, consultation with a pulmonologist for bronchoscopy or a gastroenterologist for endoscopy may also be appropriate.
- In patients who develop recurrent adverse events in the setting of ongoing or prior immunosuppressant use, an opportunistic infection should be considered in the differential diagnosis.

Additional details on the safety of nivolumab and ipilimumab, including results from clinical studies, are available in the IB.

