5.9 Discontinuation Criteria

Treatment should be permanently discontinued for the following:

 Any Grade 2 drug-related uveitis or eye pain or blurred vision that does not respond to topical therapy and does not improve to Grade 1 severity within the re-treatment period OR requires systemic treatment

Amendment9 09NOV2021 Page 30 of 77

- Any Grade 3 non-skin, drug-related adverse event lasting > 7 days, with the following exceptions for drug-related laboratory abnormalities, uveitis, pneumonitis, bronchospasm, diarrhea, colitis, neurologic adverse event, hypersensitivity reactions, and infusion reactions
 - Grade 3 drug-related uveitis, pneumonitis, bronchospasm, diarrhea, colitis, neurologic adverse event, hypersensitivity reaction, or infusion reaction of any duration requires discontinuation
 - Grade 3 drug-related laboratory abnormalities do not require treatment discontinuation except those noted below
 - Grade 3 drug-related thrombocytopenia > 7 days or associated with bleeding requires discontinuation
 - Any drug-related liver function test (LFT) abnormality that meets the following criteria require discontinuation:
 - AST or ALT > 8 x ULN
 - Total bilirubin > 5 x ULN
 - Concurrent AST or ALT > 3 x ULN and total bilirubin > 2 x ULN
- Any Grade 4 drug-related adverse event or non-hematological laboratory abnormality, except for the following events which do not require discontinuation:
 - o Isolated Grade 4 amylase or lipase abnormalities that are not associated with symptoms or clinical manifestations of pancreatitis and decrease to < Grade 4 within 1 week of onset.
 - Isolated Grade 4 electrolyte imbalances/abnormalities that are not associated with clinical sequelae and are corrected with supplementation/appropriate management within 72 hours of their onset
- Any dosing interruption lasting > 6 weeks with the following exceptions:
 - Dosing interruptions to allow for prolonged steroid tapers to manage drug-related adverse events are allowed. Prior to re-initiating treatment in a subject with a dosing interruption lasting > 6 weeks, the Investigator must be consulted. Tumor assessments should continue as per protocol even if dosing is interrupted

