APPENDIX F: ECI Management Algorithm

A general principle is that differential diagnoses should be diligently evaluated according to standard medical practice. Non-inflammatory etiologies should be considered and appropriately treated.

Corticosteroids are a primary therapy for immuno-oncology drug-related adverse events. The oral equivalent of the recommended IV doses may be considered for ambulatory patients with low-grade toxicity. The lower bioavailability of oral corticosteroids should be taken into account when switching to the equivalent dose of oral corticosteroids.

Consultation with a medical or surgical specialist, especially prior to an invasive diagnostic or therapeutic procedure, is recommended.

The frequency and severity of the related adverse events covered by these algorithms will depend on the immuno-oncology agent or regimen being used.

Where I-O therapy is referred, it means Ipilimumab and Nivolumab combination therapy.

In general terms, each immune-related adverse event (irAE) should be managed as follows:

- Grade I: Continue treatment as scheduled, manage with symptomatic treatment
- Grade II: Withhold therapy with I-O until improvement to grade I or better. If patient misses
 a dose of treatment drug due to an irAE, the following dose will be given as per the original
 schedule, and there will not be "catch-up" doses (i.e. treatment with I-O should not exceed
 original 26 weeks from initiation)
- If there has been no improvement within 7 days, then steroid therapy should be initiated. Dosage should be 1-2mg/kg/day of methylprednisolone IV (or equivalent) divided in 2 daily doses. The initial dosage should be continued until irAE have improved to Grade I or better. At that time, steroid should be tapered over the course of 2 weeks to the equivalent of 20 mg/day of methylprednisolone. If there has been no exacerbation of irAE with steroid taper, once the steroid dosage is 20 mg/day, as above, I-O can be resumed. Steroids should continue to be tapered off completely over a course of 2 additional weeks.
- Grades III-IV: Interrupt therapy and start steroids as per protocol above (Grade II). I-O should be resumed as described above.

If irAE persists after 3-5 days of high-dose steroids, or if it recurs after initial improvement, consideration should be given to infliximab 5 mg/kg or mycophenolate mofetil 500-750mg three times a day.

[figure not shown]

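### Appendix F's general rule resumes both drugs after a first Grade III-IV immune-related event, including events for which Section 5.9 ends treatment permanently

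*Combined protocol and SAP*

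**What the plan says.** Appendix F starts from a rule for all immune-related events: "In general terms, each immune-related adverse event (irAE) should be managed as follows". At Grade II, dosing is withheld. If the event has not improved within 7 days, steroids are given until it is Grade I or better and then tapered over 2 weeks. If it has not flared on the taper, "once the steroid dosage is 20 mg/day, as above, I-O can be resumed". At Grades III-IV the instruction is: "Interrupt therapy and start steroids as per protocol above (Grade II). I-O should be resumed as described above". A later sentence takes the subject off study if a Grade III or IV event recurs. Organ-specific algorithms follow under seven headings, which match the list in Section 5.6: "Gastrointestinal, Renal, Pulmonary, Hepatic, Endocrinopathies, Skin, and Neurological".

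Section 5.9 lists the reasons for permanent discontinuation. Three matter here:

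- "Any Grade 4 drug-related adverse event or non-hematological laboratory abnormality, except for the following events which do not require discontinuation". The exceptions are isolated amylase or lipase rises without pancreatitis that fall below Grade 4 within a week, and isolated electrolyte disturbances without sequelae that are corrected within 72 hours.
- "Grade 3 drug-related uveitis, pneumonitis, bronchospasm, diarrhea, colitis, neurologic adverse event, hypersensitivity reaction, or infusion reaction of any duration requires discontinuation".
- "Any Grade 3 non-skin, drug-related adverse event lasting > 7 days", with laboratory abnormalities and the events named in the previous bullet handled separately.

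Section 5.6 tells the reader where to find the algorithms: "Therefore, the algorithms recommended for utilization are in Appendix G for reference". Appendix G, however, deals with infusion reactions. The algorithms are in Appendix F.

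**The concern.** For the same first event, one part of the protocol says to restart both checkpoint inhibitors and another says never to give them again. Both are worded as instructions, and nothing states which takes precedence. Appendix F's recurrence sentence strengthens the reading that a first Grade III-IV event is meant to be followed by re-dosing, because removal is reserved for a second one.

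What is at stake is patient safety, not inference. An investigator who manages a first Grade 3 uveitis or a first Grade 4 myocarditis from Appendix F alone would re-expose the patient to ipilimumab and nivolumab after an event that Section 5.9 treats as ending therapy. Section 8.6 counts the same events as unacceptable toxicity.

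**Working it through.** The plan gives no figure on this point, so the check is a comparison of texts followed by a simple frequency bound.

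**Step 1: what resumption requires in Appendix F.** The Grades III-IV line refers back to the Grade II text. The conditions are improvement to Grade I or better, steroids tapered to the equivalent of 20 mg/day of methylprednisolone, and no exacerbation on the taper. Resumption is therefore conditional, but the conditions are recovery and taper. None of them is a check against Section 5.9, and the visible Appendix F text does not mention 5.9.

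**Step 2: the two rules side by side, for a first drug-related event.**

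| Event | Appendix F general rule | Section 5.9 | Conflict? |
|---|---|---|---|
| Grade 3 uveitis, any duration | Resume after recovery and taper | Permanent stop, by name | Yes |
| Grade 4 myocarditis or clinical pancreatitis | Same | Permanent stop, Grade 4 bullet | Yes |
| Grade 3 myocarditis lasting over 7 days | Same | Permanent stop, duration bullet | Yes |
| Grade 3 myocarditis lasting 7 days or less | Same | No grade criterion met | No |
| Grade 3 skin event | Same | Outside the Grade 3 bullet | No |

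Section 5.9 has no exception for recovery in the first three rows.

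**Step 3: which events depend on the general rule within Appendix F.** Appendix E has 11 classes of events of clinical interest: pneumonitis, colitis, endocrine, hematologic, hepatic, infusion, neurologic, ocular, renal, skin and other. Seven correspond to the named algorithms, and infusion reactions are covered by Appendix G. That leaves 11 - 7 - 1 = 3 without a named algorithm: hematologic, ocular and other (myocarditis, pancreatitis, pericarditis). This is a count of missing algorithms, not of conflicts. The conflict is shown for ocular and other events. It is not shown for hematologic laboratory events, because the laboratory limb of 5.9's Grade 4 bullet covers only non-hematological abnormalities.

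**Step 4: which text is out of line.** Section 8.6 repeats the 5.9 criteria in its definition of unacceptable toxicity. Appendix G permanently discontinues for Grade 3-4 infusion reactions, as 5.9 does. Section 5.8 defers to 5.9 twice, and 5.6 describes the algorithms as recommended. The general sentence in Appendix F is the outlier and is the one to correct.

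**Step 5: how often it could matter.** Section 3.1.5 puts uveitis and pancreatitis below 1.0% of patients on nivolumab alone or with ipilimumab, without splitting by grade. The documents give no post-transplant rate and no rate for myocarditis. Assume 1.0% as a ceiling for each event:

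- One expansion cohort: 0.01 × 37 = 0.37 cases of each event.
- All four expansion cohorts: 0.01 × 148 = 1.48 cases of each event.

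These are any-grade counts; Grade 3-4 cases would be fewer.

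**The case against.** The best defence is that a careful reader already has a hierarchy. Section 5.9 is the discontinuation list, 5.8 defers to it, the algorithms are only recommended, and Appendix F presents its rule as general. Resumption is conditional and the back-referenced text is permissive. Some material cannot be checked: the seven organ figures, one figure inside the general part of Appendix F, and the investigator brochure to which 5.6 refers. The events are also rare.

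Most of this is fair, and it limits the point. It does not remove it. No sentence states the hierarchy, the Grades III-IV line itself says resumption should happen, and its conditions do not include 5.9. For events without a named algorithm, the visible Appendix F text offers nothing more specific.

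Four stronger readings are tempting and are not supported:

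- *A reader might infer that only the general rule covers uveitis, myocarditis and pancreatitis.* That holds only within Appendix F. Section 5.9 names uveitis at Grades 2 and 3 and reaches the other two through its Grade 4 and 7-day bullets. Section 5.6 adds ophthalmologic evaluation for visual symptoms.
- *A reader might infer a conflict for every organ system.* The organ figures may agree with 5.9, and the hepatic footnote, which separates delay from discontinuation, suggests that one does.
- *A reader might infer that three whole event classes are in conflict.* Step 3 shows why the hematologic class does not count.
- *A reader might infer that the Phase IIA toxicity counts are compromised.* Section 8.6 carries its own copy of the criteria, so Table A does not depend on Appendix F.

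**Conclusion.** The contradiction is real and stands in current text. For a first Grade 3 uveitis, a first Grade 4 myocarditis or clinical pancreatitis, and a Grade 3 event of the same kind lasting over 7 days, Appendix F's general rule leads to re-dosing where Section 5.9 requires a permanent stop. The general rule remains valid for Grade III events that meet no 5.9 criterion, such as skin events, most laboratory abnormalities, and unlisted events of 7 days or less.

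The expected number of affected patients is small: below 0.4 per cohort of 37 and below 1.5 per 148 for each of uveitis and pancreatitis, at any grade. This assumes that the 1.0% ceiling in Section 3.1.5 applies to each event and carries over to the post-transplant setting. For myocarditis no figure can be given. The consequence falls on the individual patient. Sample size, endpoints, stopping boundaries and analyses are unaffected, and nothing in the documents shows that sites have acted differently. The absence of an ocular, cardiac or pancreatic algorithm is read from the headings and from the list in 5.6, because the figures are not available. The correction should be made, since the wrong instruction concerns safety and is easy to put right.

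**What to change.** 1. State in Appendix F that Section 5.9 governs.
2. Replace the Grades III-IV resume sentence with: *Permanently discontinue if any Section 5.9 criterion is met; otherwise I-O may be resumed once Section 5.8 is met and steroids have been tapered to 20 mg/day without exacerbation, as described above.* The steroid clause must stay. Section 5.8 has no steroid-dose condition, so a reference to 5.8 alone would loosen the present requirement for Grade III events outside 5.9.
3. In Section 5.6, change the reference for the algorithms from Appendix G to Appendix F.

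The recurrence sentence, Section 8.6 and Table A stay as they are. The cost is a wording amendment to Appendix F and Section 5.6 and a notice to both sites. It needs no new data and no change to sample size or boundaries.

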APPENDIX G: Treatment of Nivolumab or Ipilimumab Related Infusion Reactions

Treatment of Nivolumab or Ipilimumab Related Infusion Reactions

Treatment recommendations are provided below and may be modified based on local treatment standards and guidelines as appropriate:

Since Nivolumab and ipilimumab contains only human immunoglobulin protein sequences, it is unlikely to be immunogenic and induce infusion or hypersensitivity reactions. However, if such a reaction were to occur, it might manifest with fever, chills, rigors, headache, rash, pruritus, arthralgias, hypo- or hypertension, bronchospasm, or other symptoms.

All Grade 3 or 4 infusion reactions should be reported as an SAE if criteria are met. Infusion reactions should be graded according to National Cancer Institute Common Terminology Criteria for Adverse Events (NCI CTCAE (version 4.03)) guidelines.

Treatment recommendations are provided below and may be modified based on local treatment standards and guidelines as appropriate:

- For Grade 1 symptoms: (Mild reaction; infusion interruption not indicated; intervention not indicated)
 - Remain at bedside and monitor subject until recovery from symptoms. The following prophylactic premeditations are recommended for future infusions: diphenhydramine 50 mg (or equivalent) and/or paracetamol 325 to 1000 mg (acetaminophen) at least 30 minutes before additional nivolumab or ipilimumab administrations.
- For Grade 2 symptoms: (Moderate reaction requires therapy or infusion interruption but responds promptly to symptomatic treatment [eg, antihistamines, non-steroidal anti-inflammatory drugs, narcotics, corticosteroids, bronchodilators, IV fluids]; prophylactic medications indicated for 24 hours).
 - Stop the nivolumab or ipilimumab infusion, begin an IV infusion of normal saline, and treat the subject with diphenhydramine 50 mg IV (or equivalent) and/or paracetamol 325 to 1000 mg (acetaminophen); remain at bedside and monitor subject until resolution of symptoms. Corticosteroid or bronchodilator therapy may also be administered as appropriate. If the infusion is interrupted, then restart the infusion at 50% of the original infusion rate when symptoms resolve; if no further complications ensue after 30 minutes, the rate may be increased to 100% of the original infusion rate. Monitor subject closely. If symptoms recur then no further nivolumab or ipilimumab will be administered at that visit. Administer diphenhydramine 50 mg IV, and remain at bedside and monitor the subject until resolution of symptoms. The amount of study drug infused must be recorded on the electronic case report form (eCRF). The following prophylactic premeditations are recommended for future infusions: diphenhydramine 50 mg (or equivalent) and/or paracetamol 325 to 1000 mg (acetaminophen) should be administered at least 30 minutes before additional nivolumab or ipilimumab administrations. If necessary, corticosteroids (recommended dose: up to 25 mg of IV hydrocortisone or equivalent) may be used.
- For Grade 3 or Grade 4 symptoms: (Severe reaction, Grade 3: prolonged [i.e., not rapidly responsive to symptomatic medication and/or brief interruption of infusion]; recurrence of symptoms following initial improvement; hospitalization indicated for other clinical sequelae [e.g., renal impairment, pulmonary infiltrates]). Grade 4: (life-threatening; pressor or ventilator support indicated).

Amendment9 09NOV2021 Page 69 of 77

Immediately discontinue infusion of nivolumab or ipilimumab. Begin an IV infusion of normal saline, and treat the subject as follows. Recommend bronchodilators, epinephrine 0.2 to 1 mg of a 1:1,000 solution for subcutaneous administration or 0.1 to 0.25 mg of a 1:10,000 solution injected slowly for IV administration, and/or diphenhydramine 50 mg IV with methylprednisolone 100 mg IV (or equivalent), as needed. Subject should be monitored until the investigator is comfortable that the symptoms will not recur. Nivolumab or ipilimumab will be permanently discontinued. Investigators should follow their institutional guidelines for the treatment of anaphylaxis. Remain at bedside and monitor subject until recovery from symptoms. In the case of late-occurring hypersensitivity symptoms (eg, appearance of a localized or generalized pruritus within 1 week after treatment), symptomatic treatment may be given (e.g., oral antihistamine, or corticosteroids).

Amendment9 09NOV2021 Page 70 of 77

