9.5 Procedures for AE and SAE Reporting

All Adverse Events and Serious Adverse Events (SAEs) that occur following the subject's first dose of therapy on Day 1 of Week 1 of combined checkpoint therapy in the study through 100 days of discontinuation of dosing or until the start of a subsequent systemic anti-cancer therapy, if earlier, must be reported to BMS Worldwide Safety, and according to local regulations. All serious adverse events (SAE) regardless of causality must be reported to the PI, (within 24 hours) and the research coordinator for notification of Hackensack University Medical Center's IRB.

The local IRB must be informed of any serious, unexpected, or alarming adverse events that occur during the approval period involving a subject within seven days of occurrence, or sooner if local guidelines apply. Any deaths of subjects require immediate (within 24 hours) reporting.

Sponsor generated reports of adverse events occurring at other investigative sites within fourteen days of receipt if the event is definitely related or possibly related to the research protocol as deemed by the sponsor lead investigator, and/or the DSMB.

Intensity for each adverse event, including any lab abnormality, will be determined by using the NCI CTCAE, version 4.03, as a guideline, wherever possible. The criteria are available online at http://evs.nci.nih.gov/ftp1/CTCAE/CTCAE 4.03 2010-06-14 QuickReference 8.5x11.pdf.

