9.6 Assessment of Toxicity

Common Terminology Criteria for Adverse Events (CTCAE) will be used for the assessment and grading of all toxicities experienced by patients enrolled into this study (http://ctep.cancer.gov/forms/CTCAE Index.pdf)

If the nature of the adverse experience is listed in the CTCAE, the maximum grade will be reported.

If the adverse experience is not listed in the NCI CTCAE Common Terminology Criteria Adverse Events, report the toxicity grade using the following criteria:

- Grade 1 = Mild: an adverse experience which is easily tolerated by the patient, causing minimal discomfort and not interfering with everyday activities.
- Grade 2 = Moderate: an adverse experience which is sufficiently discomforting to interfere with normal everyday activities.
- Grade 3 = Severe: an adverse experience which is incapacitating and prevents normal everyday activities.

- Grade 4 = Life Threatening: an adverse experience which places the patient at immediate risk of death.
- Grade 5 = Death

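### Appendix G withholds drug only for the visit when a grade 2 infusion reaction recurs after restart, although its next bullet makes that recurrence grade 3, which requires a permanent stop

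*Combined protocol and SAP*

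**What the plan says.** Appendix G handles infusion reactions by grade.

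- **Grade 2 branch.** The infusion is stopped and symptoms are treated. If it was interrupted, staff are to "restart the infusion at 50% of the original infusion rate when symptoms resolve". For a second episode the text reads: "If symptoms recur then no further nivolumab or ipilimumab will be administered at that visit". Diphenhydramine and observation follow, and the branch closes with premedication advice: "The following prophylactic premeditations are recommended for future infusions". That advice is not limited to patients whose restart succeeded.
- **Grade 3 or 4 branch, the next bullet.** Its description of grade 3 includes "recurrence of symptoms following initial improvement". Its action is: "Nivolumab or ipilimumab will be permanently discontinued".
- **Grading.** Appendix G states: "Infusion reactions should be graded according to National Cancer Institute Common Terminology Criteria for Adverse Events". Under Section 9.5, the intensity of each adverse event "will be determined by using the NCI CTCAE, version 4.03, as a guideline, wherever possible". Section 9.6 adds that for events listed in the CTCAE "the maximum grade will be reported".
- **Discontinuation.** Section 5.9 requires permanent discontinuation for a grade 3 drug-related infusion reaction, however long it lasts.
- **Stopping rules.** Section 8.6 repeats that item in its list of unacceptable toxicities for Phase IIA. The Phase Ib rule counts only non-hematologic toxicity of grade 4 or higher.

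**The concern.** The restart is allowed only after symptoms have resolved, so any recurrence after it follows improvement. That is the situation the next bullet describes as grade 3. One bedside event thus has two instructions: withhold for the day, or stop for good. The sentence that staff are reading when the event happens gives the weaker one and does not send them to the grade 3 branch.

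The first thing at stake is the patient. A site relying on the grade 2 branch could bring back a patient who must stop under Section 5.9. The second is the Phase IIA count. A site working in the grade 2 branch may leave the reaction recorded as grade 2, in which case Section 8.6 does not count it.

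**Working it through.** **1. The texts side by side**

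| Step | Grade 2 branch | Grade 3 branch, 5.9 and 8.6 |
|---|---|---|
| Symptoms resolve, infusion restarted | Half rate | Not addressed |
| Symptoms return | No more drug that day | Meets the grade 3 description |
| Later visits | Premedication advice, no stop stated | Permanent discontinuation |
| Phase IIA count | Silent | Counted as unacceptable toxicity |

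If every recurrence ends treatment, limiting the instruction to that visit serves no purpose. The two columns cannot both govern later visits.

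**2. Doses at issue**

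Section 5.3 schedules 12 nivolumab and 6 ipilimumab doses, with both drugs given in Week 1. After a Week 1 recurrence, 12 − 1 = 11 nivolumab and 6 − 1 = 5 ipilimumab doses remain. This is a ceiling.

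**3. Reproducing the plan's own figures**

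Inputs, all from Section 8.6: Table A (stop at 1 toxicity in 2 patients, 2 in 5, 3 in 9, 4 in 13, 5 in 17, 6 in 21, 7 in 25, 8 in 29, 9 in 33, 10 in 37); looks after each patient from 2 to 37; acceptable rate 0.25 and unacceptable rate 0.30.

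Let d(n, j) be the probability that the cohort is still open after patient n with j counted toxicities, and p(n) the chance that patient n has one. Then

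d(n, j) = (1 − p(n)) × d(n−1, j) + p(n) × d(n−1, j−1).

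At each look, the mass with j at or above the Table A count for the next listed n is removed. The stopping chance is the total removed, including at patient 37.

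- Rate 0.25: 0.772, expected sample size 13.9. Table B, high boundary: 0.772 and 13.9.
- Rate 0.30: 0.897, expected sample size 9.9. Table B, high boundary: 0.897 and 9.9.

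Looking only at the ten listed sample sizes gives the same crossing probabilities but expected sizes of 14.1 and 10.2. Table B therefore rests on a look after every patient.

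**4. One event, uncounted versus counted**

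Set p(n) = 0 (uncounted) or 1 (counted) for one patient and 0.25 for all others. Seen from the start of the cohort:

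| Position of the patient | Uncounted | Counted | Difference |
|---|---|---|---|
| 1–2 | 0.696 | 1.000 | 0.304 |
| 3–5 | 0.734 | 0.886 | 0.152 |
| 20 | 0.755 | 0.821 | 0.066 |
| 37 | 0.766 | 0.789 | 0.023 |

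Check: weighting each pair by 0.75 and 0.25 must return 0.772. For patients 1–2, 0.75 × 0.696 + 0.25 × 1.000 = 0.772. For patients 3–5, 0.75 × 0.734 + 0.25 × 0.886 = 0.772.

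Given that the cohort is still open when the patient enters, again with a look after every patient, the pairs are 0.495 and 0.784 (patient 5), 0.218 and 0.428 (patient 20), 0.068 and 0.204 (patient 30), and 0.000 and 0.099 (patient 37).

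**5. Overall effect under an assumed frequency**

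The documents give no recurrence rate. As an assumption, let a share q of patients without another counted toxicity have such a recurrence, so that counting all of them rather than none moves the rate from 0.25 to 0.25 + 0.75q. For q = 1% the rate is 0.2575 and the stopping chance 0.795; for q = 2%, 0.265 and 0.816; for q = 5%, 0.2875 and 0.872. The comparison is with 0.772, and it is an upper bound for each q because it supposes that every such event would otherwise be misgraded.

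**The case against.** The plan already holds the right answer. The grade 3 description stands directly below the sentence at issue, and Section 5.9 states the stop without qualification. Appendix G calls its steps recommendations open to local modification, and on the day itself both branches stop the infusion. The grade 2 branch nowhere says that a patient with a recurrence may be re-dosed, and its premedication advice can be read as meant for patients whose restart succeeded.

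Much of this stands. Re-dosing is an inference from the visit-only limit and the unrestricted premedication advice, and it requires 5.9 to be overlooked. But a correct rule elsewhere does not make this sentence correct. Sections 5.9 and 8.6 carry no allowance for local modification, so the appendix cannot soften them.

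A reader might infer more: that following the visit-only sentence by itself takes the event out of the Phase IIA count. The documents do not support that. Counting under 8.6 depends on the recorded grade and attribution, not on how long drug is withheld, and the sentence says nothing about grade. A site that withholds drug for one visit but grades as Appendix G and Section 9.6 require still records grade 3, and the event is counted. An uncounted event needs a further step: leaving the reaction at grade 2.

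The paired figures also show what any single missed toxicity does to Table A. They are not specific to infusion reactions.

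**Conclusion.** The sentence is wrong as written, and the severity is minor. It conflicts with the grade 3 branch of Appendix G and with the mandatory stop in Section 5.9. The main consequence is possible re-dosing of a patient who must stop, up to the 11 and 5 doses above.

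The effect on counting is secondary and depends on misgrading. Where it occurs, a single event decides a cohort by itself only in patients 1–2, and its influence shrinks with position. Phase Ib stopping is unaffected, because a grade 3 reaction is below its threshold.

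The per-event figures assume a rate of 0.25 for all other patients, independence between patients, and a look after every patient from 2 to 37. The overall effect on cohort stopping is probably small: Appendix G regards infusion reactions as unlikely, and misgrading is needed as well. That is a judgement, since no recurrence rate is given.

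**What to change.** In the grade 2 branch of Appendix G, replace the sentence on recurrence with: *If symptoms recur after the restart, the reaction is grade 3: give no further study drug, follow the grade 3 instructions below and permanently discontinue per 5.9.* Limit the closing premedication advice to grade 2 reactions that do not recur. A pointer to Section 8.6 is optional, because that section already lists grade 3 infusion reactions.

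The cost is a small wording change, with no added patients or procedures and no change to the boundary. The possible downside is slightly more counted events and so a slightly higher chance of stopping a Phase IIA cohort. The later doses lost to a patient with a recurrence are doses that 5.9 already rules out.
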